5.3.2. Study Specific Tests and Procedures

Measurements

Height

Height will be measured in centimeters to the nearest centimeter using a stadiometer, without shoes, and facing away from the wall.

Weight

Weight will be obtained using a zeroed electronic scale. Participants will be weighed without shoes or outer garments (sweaters, coats off) at this visit and all subsequent follow-up visits to the nearest tenth of a kilogram.

Waist circumference

Waist circumference will be measured after subject removes shoes and places feet hip distance apart. This will be taken against the skin, not on top of clothing. The point of measurement will be determined by locating a bony landmark, the right iliac crest. The CRC will make a horizontal mark with a pen or marker above their fingers to indicate the spot directly above the top of the iliac crest. The CRC will place the tape around subject's midsection at the level of the mark, maintaining a horizontal plane around the abdomen. This measurement will be taken and recorded 3 times and averaged. The tape measure will be released between each measurement.

BMI

Body mass index (BMI) will be calculated from these measurements (BMI = weight [kg] / ht [m]²)

Blood Pressure

Blood pressure measurements will be taken on the right arm (unless contraindicated) with an appropriate size cuff while participants are seated with the right arm supported at mid-atrial level. Participants are asked to refrain from eating, smoking, and exercise for at least 30 minutes prior to blood pressure measurements, and to sit quietly for at

Genetic Risk Testing and Health Coaching for CHD and T2D

Duke IRB# Pro00039569 NCT01884545

least 5 minutes before the blood pressure measurement. Two measurements of BP will be taken with a two minute rest period between the measures, and averaged.

Blood collection for genetic testing

Participants in each of two genetic testing arms will complete venipuncture for peripheral blood sample collection for genetic testing of validated CHD RS10757274 and T2D RS7903146, RS1801282, RS5219 risk variants.

Samples will be sent to Duke University Clinical Molecular Diagnostics Laboratory, which is CLIA-certified. DNA extraction will be performed as well as real time PCR allelic discrimination assays for RS7903146, RS1801282, RS5219, and RS10757274 (Appendix P.). Results (genotyping of alleles for SNPs of interest) will be returned by subject studyID number to the site research staff for entry into the REDCap database. Remaining blood samples will be retained by the lab until the end of the study, at which time they will be discarded.

Standard Risk Assessment (SRA) for CHD and T2D (need to take place no later than 4 weeks post randomization)

The SRA has been developed for this study based on the Framingham risk assessment and other known risk factors for CHD and T2D. The SRA consists of: FBG, age, gender, BMI, total cholesterol, HDL, BP, family history (number of first-degree relatives who have CHD (and age at diagnosis) or T2D, self-reported), and smoking (self-reported). A Framingham Risk Score and Diabetes Risk Score will be calculated for each patient along with other well-validated CHD and T2D risk factors, and all will be reviewed at the risk counseling visit. This method of presenting genetic risk data to patients has successfully been used for over 400 clinical study patients to be used by the provider (Appendix K., L., M., N.).

Health Coaching(HC) Intervention. Upon completion of their individual SRA Visit, participants in the two groups that include health coaching will be assigned to a trained health coach for a period of 5 months (n=200). At the SRA, the participant will fill out a “Current & Desired States Form” (Appendix C.). Then the participant will be given a folder containing information about what HC is, how the calls will be structured, and preparation materials for the calls (Appendix E.). An initial telephone call (60-75 minutes in length) with the coach will consist of a discussion on the role of the health coach and participant, the logistics of the sessions, and a discussion about the participant’s self-assessment of health perceptions and goals. This self-assessment creates the foundation for the personalization of the behavioral intervention. From this point, the

Genetic Risk Testing and Health Coaching for CHD and T2D

Duke IRB# Pro00039569 NCT01884545

participant schedules the remaining 9 biweekly sessions (30-45 minute in length) , for a total of 10 coaching calls over 5 months. All 10 telephone calls will be recorded for quality control and qualitative analysis purposes.

Self-discovery (initial) session. In the first HC call, participants are led through a process of self-discovery wherein they create a vision of health. The coaches assist participants in a self-assessment process to compare their personal goals to their current satisfaction in multiple domains of their lives. Areas that are discrepant (Appendix C.) are further explored for readiness to change. Participants then prioritize where to begin. They are encouraged to make skillful decisions that are congruent with their individual values, long-term vision and sense of purpose. Heavily supported by theory, participants are more likely to create self-sustaining agendas for themselves when they have considered the greater perspective of their lives. The coaching agenda, priorities and specific goals will be set by the participant; however the coach will regularly ask participants about self-assessment in terms of risk reduction via diet and exercise. Committing to small action steps on a biweekly basis, participants move toward self-identified health goals. Results of the self-assessment provide initial motivation for lifestyle behavior change.

During the initial call, participants are taught how to prepare for the HC sessions. They previously had received tools and information for preparation, including a “coaching prep-form”, contained in the HC Packet (Appendix E.). The form is optional for the participant to use, and is organized to assist clients in briefly noting discussion points for the call including: successes since last call; obstacles encountered; problem-solving approaches tried; outcomes; upcoming potential obstacles; resources needed; small action-step commitments to be accomplished before the next call. While the general process is the same for all participants, the coaching content is highly tailored and personalized according to the individual’s needs, readiness to change, and personal vision of health.

Additional biweekly calls. HC calls then follow the general template of the coaching prep form. All HC sessions begin with a brief check-in, reporting on specific action steps from the preceding week(s). Participants are trained to note success first, then to problem-solve and explore solutions for upcoming obstacles. Importantly, they learn from failed problem-solving attempts, which are non-judgmentally framed as “experiments” necessary for true learning. Non-judgmental framing is essential to maintaining rapport and encouraging clients to experiment with solutions without fear of failure. Participants then commit to new action steps toward their goals to be accomplished before the next call, and clarify what resources they will need to accomplish them. Of note, the health coaches will be blinded to the participants’ genetic risk results; however, participants may choose to disclose them to the coaches, mimicking actual utilization of this information (Appendix D.).

Table 2. Study Measures	Baseline	6 wks	3 mos	6 mos	12 mos
Eligibility Screen & Informed Consent	X				
Demographic Questionnaire	X				
Family history of CHD & T2D	X				
Blood collection for genetic testing	X				
Primary Outcomes: Behavioral					
Wheel of Health	X	X		X	
Dietary Intake (NCI Multifactor Screener)	X		X	X	X
Physical Activity (SBAS)/Wellness Programs	X		X	X	X
Smoking Status	X		X	X	X
Medication Adherence (Morisky 4)	X	X		X	X
Primary Outcomes: Clinical					
Height for BMI calculation	X				
Weight	X			X	X
Waist Circumference	X			X	X
Blood pressure	X			X	X
Medications	X			X	X
Lab tests (fasting glucose, total cholesterol, HDL, LDL, triglycerides)	X				X
Fitness Status (Air Force Fitness Score)	X				X
Risk Status (FRS and T2D Risk Score)	X				X
Adverse Events Assessed				X	X
Potential Mediators					
Perceived Risk for CHD & T2D	X	X		X	
Worry, Self-efficacy	X	X		X	
Patient Activation	X	X	X	X	X
Stages of Change	X	X	X	X	
Psychosocial Risk Factors: Depression (BDI), stress level (PSS) social isolation (social support item) Hostility (cook-medley)	X X			X	

6. Adverse Events

An adverse event (AE) is the development of an unfavorable or unintended sign, symptom, disease or the deterioration of a pre-existing condition that occurs while a patient is enrolled in a clinical trial, whether the event is considered related or unrelated to the study interventions. An adverse event is any adverse change from the subject's baseline condition, including any clinical or lab test abnormality that occurs during the course of research after intervention has started.

6.1. Adverse Event Reporting

If at any time during the study protocol a subject develops an adverse event), he/she should first contact their primary care physician. In addition, the site PI and site coordinator as well as the coordinating center PI will be available to answer questions. The site coordinator will assess AEs at the 6 and 12-month visits and will record all reported events in the adverse event log including the subject's ID, date, and event description, duration and intensity. CRC will inform the principal investigator, who will consult with co-investigators on the action that should be taken. The action and date of implementation will also be recorded in the adverse event log. The investigators will participate in classifying events as "serious" or "non-serious" (see section 6.2), as well as "non-attributable," "possibly attributable" or "attributable" to the intervention (unlike a pharmaceutical trial where known side effects exist, the classification of "expected" vs. "unexpected" is inappropriate for this behavioral intervention).

Information for the adverse event must be recorded on the appropriate page of the case report form (CRF). Only data on AEs grade 3 and higher will be recorded in the database. AE assessment will be done according to CTCAE v.4 (http://evs.nci.nih.gov/ftp1/CTCAE/CTCAE_4.03_2010-06-14_QuickReference_5x7.pdf

Note: As a behavioral intervention study there are no expected AEs. However, as a precaution since the Beck Depression Inventory (BDI) is administered at Baseline and 6 Month Visits the following procedures will be followed.

As a part of the baseline and follow-up surveys, subjects will complete a depression assessment (Beck Depression Inventory). Answers to the following question need to be closely monitored:

CRC will review the survey immediately after subject has completed it at baseline and 6 month visits. If the subject indicated suicidal ideations on the related item he/she will be referred to a therapist for evaluation.

Referrals for psychological care will be completed by the CRC at Travis site according to the David Grant Medical Center policies and procedures outlined in their site protocol.

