9.6. Protection of Privacy

Patients will be informed of the extent to which their confidential health information generated from this study may be used for research purposes. Following this discussion, they will be asked to sign the HIPAA form and informed consent documents. The original signed document will become part of the patient's medical records, and each patient will receive a copy of the signed document. The use and disclosure of protected health information will be limited to the individuals described in the informed consent document.

It is the responsibility of the research staff to ensure that protocol subjects received, understands, and signs the informed consent document before enrolling the patient onto this trial. Personnel must provide a HIPAA form and obtain acknowledgment before the subject participates in this study.

10. Risk/Benefit Assessment

10.1. Risks of Drawing Blood:

Risks associated with drawing blood from the subjects arm include minimal discomfort and/or bruising. Infection, excess bleeding, clotting, or fainting are also possible, although unlikely.

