10.2. Potential Risk of emotional reactions to the genetic tests results

Participants may have emotional reactions to learning that they do- or do not— carry a gene change for heart disease or diabetes. Participants who feel distressed will be directed to the site study doctor and he may refer them to a genetic counselor or other provider for further assistance as necessary

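### Adverse events of every grade are logged, but only grade 3 and higher enter the database and no adverse event analysis is planned, so low-grade harm will not be compared by group under the plan.

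*Combined protocol and SAP*

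**What the plan says.** Section 6 defines an adverse event broadly, as any unfavorable change, related or not. On assessment times, section 6.1 says: "The site coordinator will assess AEs at the 6 and 12-month visits". The coordinator is to "record all reported events in the adverse event log including the subject's ID, date, and event description, duration and intensity". Investigators then class each event as serious or non-serious, and as non-attributable, possibly attributable or attributable. Adverse event information also goes on the case report form, with no grade limit stated. Grading follows CTCAE v.4.

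The next step narrows this: "Only data on AEs grade 3 and higher will be recorded in the database". The only nearby rationale is the note that "As a behavioral intervention study there are no expected AEs".

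Section 10 nevertheless names foreseeable harms. Section 10.1 says: "Risks associated with drawing blood from the subjects arm include minimal discomfort and/or bruising". It adds infection, excess bleeding, clotting and fainting as possible but unlikely. Section 10.2 says: "Participants may have emotional reactions to learning" their genetic result.

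Section 7.1 makes REDCap the database that is reviewed, declared complete and locked. Section 8.2 covers the behavioral, metabolic and mediation analyses and contains no analysis of adverse events.

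**The concern.** Genetic risk counseling and health coaching will be judged on harm as well as benefit. The plan pays most of the cost of collecting low-grade events: they are elicited, described, timed, graded and attributed. It then leaves them out of the locked data. An event the investigators themselves judge attributable to the intervention drops out of any planned comparison if it is grade 1 or 2 and not serious. Section 6.2 does not close the gap, because its prompt alerts concern serious events that are related to the study or fatal.

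At stake is the reading of the final report. A table built from the database could show few or no events in every group, and a reader could take that as evidence about harm in general when it speaks only to grade 3 and higher.

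**Working it through.** **1. Follow a low-grade event through the plan.**

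| Step | Section | Event of grade 1 or 2 | Event of grade 3 or higher |
|---|---|---|---|
| Asked about at 6 and 12 months | 6.1 | Yes | Yes |
| Entered in log with subject ID and intensity | 6.1 | Yes | Yes |
| Attribution classified | 6.1 | Yes | Yes |
| Recorded on case report form | 6.1 | Yes | Yes |
| Entered in the database | 6.1, 7.1 | No | Yes |
| Analysis by group specified | 8.2 | No | No |

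The loss comes from a stated rule at the fifth step, joined to silence at the sixth.

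**2. Which named harms are affected.** Minimal discomfort and bruising (10.1) are mild in the protocol's own words, so the rule would exclude them if they were reported. Section 10.2 gives no severity for emotional reactions, and no grade is given for fainting, so neither can be placed below grade 3 from the documents.

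**3. What covers emotional reactions otherwise.** Table 2 lists worry at baseline, 6 weeks and 6 months. Section 6.1 places the BDI at baseline and 6 months. Perceived stress (PSS) is also listed, though its row is broken in the text. Section 7.1 administers surveys through REDCap, with no grade threshold. Section 8.2 uses worry only as a mediator and plans no between-group harm comparison of any of the three.

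**4. Size.** The plan states no adverse event rate and no safety power, so there is no figure to reproduce. The following is an illustration on assumed rates only.

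Input from section 5.1: 250 enrolled, so 250/2 = 125 per level of the genetic factor if groups are equal. Assumed: any-grade rates p0 and p1, and a share s of events that reach grade 3, the same on both sides, from 2% to 20%.

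Power (two-sided 0.05) = Φ[(|p1 − p0| − 1.96·se0)/se1], with se0 = √(p̄(1 − p̄)·2/125) and se1 = √((p0(1 − p0) + p1(1 − p1))/125).

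For 10% v 20%: p̄ = 0.15; se0 = √(0.1275 × 0.016) = 0.0452; se1 = √(0.25/125) = 0.0447; (0.10 − 0.0885)/0.0447 = 0.26; power = 0.60.

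For grade 3 and higher, replace p0 and p1 by s·p0 and s·p1. The chance of no such event on either side is (1 − s·p0)^125 × (1 − s·p1)^125.

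| Any-grade rates | Power, all grades | Expected grade 3+ events, s = 2% | Expected grade 3+ events, s = 20% | Power, grade 3+ only | Chance of none on either side |
|---|---|---|---|---|---|
| 10% v 20% | 0.60 | 0.25 v 0.50 | 2.5 v 5.0 | 0.05 to 0.15 | 47% to under 1% |
| 5% v 15% | 0.75 | 0.125 v 0.375 | 1.25 v 3.75 | 0.05 to 0.20 | 61% to under 1% |
| 10% v 25% | 0.88 | 0.25 v 0.625 | 2.5 v 6.25 | 0.06 to 0.25 | 42% to under 1% |

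In the last two columns, the first value is for s = 2% and the second for s = 20%. The normal approximation is rough at such small counts. The table also uses everyone enrolled; with the 15% attrition allowed in section 8.1, about 250 × 0.85/2 = 106 per side would remain. The direction is clear, but the size depends wholly on the assumed rates.

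**The case against.** A reader might infer that low-grade harm cannot be compared by group at all. The documents do not support that. The log carries subject ID and intensity, the case report form carries adverse event information, and section 7.3 requires retention of source documents. The events can be linked to allocation; they are simply neither entered nor planned for analysis.

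A reader might also infer that the trial is built to show no harm. That goes too far. Grade 3 and higher events are entered, related serious events and deaths are escalated under section 6.2, and the threshold is the same in every group. It reduces sensitivity without dictating a null result.

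Three further points stand:
- The harm most specific to the genetic arms, emotional reaction, has measures in all groups through worry, BDI and PSS. This cover is partial: worry and the BDI have no 12-month assessment, no harm comparison is planned, and none of the scales captures physical events or attribution.
- Bruising is a weak example. The genotyping draw is a baseline procedure in the two genetic groups only, so the difference is known in advance. One sentence in section 6 limits adverse events to changes after the intervention has started. A minor bruise is also unlikely to be reported first at 6 months.
- Minor exercise injury in coached participants is plausible, but section 10 does not list it.

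Finally, logging everything and entering selectively is a coherent workflow, and a severity threshold is a legitimate choice in a behavioral trial. What this does not answer is that events judged attributable are left out along with the rest, although entering them would cost little.

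**Conclusion.** The point holds as a modest improvement to the plan. Under the stated rule and with section 8.2 as written, adverse events below grade 3 will not be compared by randomized group, including any classed possibly attributable or attributable. The consequence is lower sensitivity to low-grade harm, partly offset for emotional reactions by survey scores already in REDCap. The number of events affected cannot be estimated from the documents. The power figures illustrate direction only, and rest on assumed event rates, an assumed share reaching grade 3, and equal groups of 125. No conclusion about benefit is affected. What is affected is how far a statement of no harm can reach.

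**What to change.** Enter all logged adverse events in REDCap with grade, date and attribution. Add to section 8.2 a descriptive table by randomized group: participants with at least one event and number of events, by grade and attribution. Report worry, BDI and PSS by group beside it. No hypothesis test is needed.

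If full entry is refused, the minimum is to enter events of any grade classed possibly attributable or attributable. That version needs a caveat: attribution is a judgement that may depend on knowing the group, and the site coordinator who records the events also tells participants their assignment. Entering all events avoids selecting on that judgement.

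If neither is done, the report should limit any statement of no harm to grade 3 and higher.

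The cost is transcription from an existing log and case report form for 250 participants, plus a short set of descriptive tabulations. It needs no new assessments or staff. It does not change when events are asked about, so short-lived events that participants no longer report at 6 or 12 months would still be missed.

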5.3. Schedule of Events

5.3.1. Visit Overview

Baseline visit:

[figure not shown]
Informed consent will be obtained and documented. Inclusion and exclusion criteria will be verbally verified with participant and date of consent will be documented on the Case Report Form (CRF, Appendix A.). Height, weight, waist circumference, and blood pressure will be measured by CRC and documented on CRF. Refer to section 5.3.2. Study Specific Tests and Procedures for methods of obtaining height, weight, waist circumference, and blood pressure.

Most recent lab results (FBG or HbA1c, TC, TRIG, HDL, LDL, last PHA,) and current medications will be obtained from the EMR. Last fitness score will be obtained from a separate database, outside of the EMR. Participants who are not active duty will not have PHA with fitness scores. All variables measured directly or obtained from EMR will be entered into REDcap by CRC. Subjects randomized to the two genetic arms will have blood collected and sent for testing at Duke University Clinical Molecular Diagnostics Laboratory. Female subjects will be asked if they are currently pregnant and this will be documented (Note: the purpose of collecting pregnancy information is to account for potential confounders later in analysis; not for exclusion criteria). Participants will be registered in REDCap database. They will complete the baseline survey during their clinic visit (at a clinic computer).

Genetic Risk Testing and Health Coaching for CHD and T2D

Duke IRB# Pro00039569 NCT01884545

Fig.1. Study Schema

Genetic Risk Testing and Health Coaching for CHD and T2D

Duke IRB# Pro00039569 NCT01884545

Randomization:

Randomization will take place to *one* of the following:

1. Standard Risk Assessment (SRA) only;
2. SRA plus Health Coaching (SRA+HC);
3. SRA plus Genetic Risk Counseling (SRA+GRC); *or*

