4. SRA+HC+GRC

Random assignments will be generated using a standard random number generator with uniform distribution to the four groups by the Clinical Genomics Study Unit (CGSU) data manager. The research staff (CRC at site) will use this randomization schema to inform participants of their group assignment.

Follow up visits:

6-week and 3-month – At 6 weeks and 3 months after the baseline visit, participants will be asked to complete selected surveys online (Table 1). The 6 week survey must be completed after the counseling visit and before Health Coaching begins.

6-month – Six months from the baseline visit, participants will return to the clinic to have weight, BP and waist circumference measured (same procedures as baseline visit). Medications will be reviewed and AE's assessed.

Female subjects will be asked if they are currently pregnant and this will be documented.

They will also complete the required surveys as listed, either before their scheduled visit or during their visit at the clinic.

12-month- Twelve months from the baseline visit, participants will return to the clinic for a final visit to have weight, BP and waist circumference measured (same procedures as baseline visit). Medications will be reviewed and AE's assessed.

Lab values from the EMR will be documented for fasting glucose, TC, HDL, LDL, TRIG CRC will check in EMR prior to each subject's 12-month visit. If lab values as stated above are not available from the last 6 months of study participation , then a lipid panel (TC, HDL, LDL, TRIG) and either a FBG or HbA1c will be ordered. Female subjects will be asked if they are currently pregnant and this will be documented.

They will also complete the required surveys as listed, either before their scheduled visit or during their visit at the clinic.

Window of ±one week were allowed for all follow up visits. In order to maximize power and considering

Genetic Risk Testing and Health Coaching for CHD and T2D

Duke IRB# Pro00039569 NCT01884545

recent findings on the stability of metabolic clinical markers absent behavior change, statistical analyses will employ extended inclusion windows for study time-points. Statistical analyses will include: +/-3 weeks for the 6 week survey, +/-7 weeks for the 3 month survey, and +/-11 weeks for the 12 month survey.

Table 1.

STUDY VISITS	GROUP 1	GROUP 2	GROUP 3	GROUP 4

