7.1. Data Entry

The research coordinators, data manager and PI are responsible for ensuring that data abstraction (information required by the protocol) is completed in a timely manner for every subject enrolled on study. De-identified

subjects' data will be entered by the site CRC into a secure electronic database (REDCap) by CGSU data managers. REDCap is a secure and HIPAA compliant web-based application .The data are backed up daily and stored on a secure server managed by Duke University School of Medicine IT Department. The PI, study coordinators and the CGSU data management staff are the only key personnel who will have access to the password-protected database. Subjects' surveys will also be administered through REDCap. Subjects will be assigned access to the system upon study registration and will be provided with the necessary directions by the study coordinators. The CGSU data management staff and PI will systematically review the information entered into the database. Errors or omissions will be documented and maintained with the study files. When the database has been declared complete and accurate, the database will be locked.

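### Sections 5.3.1 and 6.1 are inconsistent on the 6-month BDI: its suicidality review is tied to the visit, but the surveys may be completed before it

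*Combined protocol and SAP*

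**What the plan says.** Section 6.1 (Adverse Event Reporting) sets out a precaution built on the BDI. It states that "the Beck Depression Inventory (BDI) is administered at Baseline and 6 Month Visits", and then that "CRC will review the survey immediately after subject has completed it at baseline and 6 month visits". A participant who endorses the suicidality item is referred to a therapist. Referrals follow the medical center's policies, as outlined in its site protocol.

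The same section makes the BDI part of the survey package: "As a part of the baseline and follow-up surveys, subjects will complete a depression assessment (Beck Depression Inventory").

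Section 5.3.1 (Visit Overview) says when that package is completed. At baseline: "They will complete the baseline survey during their clinic visit (at a clinic computer"). At 6 months: "They will also complete the required surveys as listed, either before their scheduled visit or during their visit at the clinic". The 6-month text does not treat the BDI separately.

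Section 7.1 (Data Entry) says that participants' "surveys will also be administered through REDCap", a web-based system, and that "Subjects will be assigned access to the system upon study registration". It gives study coordinators access to the database. It also has data management staff and the PI review the entered data systematically, with no timing stated.

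**The concern.** The coordinator's review is the step that the protocol describes between the suicidality item and a therapist referral. It is worded by reference to a clinic visit, when coordinator and participant are in the same place. The 6-month survey rule also allows completion elsewhere, earlier, with no coordinator present.

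A participant who uses that option could report suicidal ideation from home. A coordinator who regards the review as part of the visit might not open the answer until the participant arrives. What is at stake is the promptness of a referral for a person at possible risk. No endpoint, estimate or test is affected.

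**Working it through.** No arithmetic applies; the check is a comparison of the sections.

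1. **Is the BDI among the 6-month surveys?** Yes. Section 6.1 makes it part of the follow-up surveys and names the 6-month visit. The psychosocial row of Table 2, although its columns are partly broken in the supplied copy, is consistent with baseline and 6 months.

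2. **May those surveys be completed before the visit?** Yes. Section 5.3.1 says so and makes no exception for the BDI.

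3. **Is off-site completion realistic?** Yes. Surveys run in web-based REDCap, participants have access from registration (section 7.1), an email address and internet access are inclusion criteria (section 3.2), and the 6-week and 3-month surveys are completed online (section 5.3.1 and Table 1).

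4. **Does baseline have the same problem?** No. The baseline survey is done at a clinic computer during the visit. Of the two BDI administrations, only the 6-month one is involved.

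5. **How early could a survey be submitted?** Not stated. The window of one week either side in section 5.3.1 applies to follow-up visits. No limit is given on how long before the visit the surveys may be done.

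6. **What would bring an early answer to the coordinator's attention?** Coordinators can see the database, so they are able to look. The supplied text describes no alert, no scheduled check and no contact procedure. The systematic review in section 7.1 has no timing and is assigned to data management staff and the PI. The site protocol is cited for making referrals, not for when the survey is read.

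7. **How can section 6.1 be read for a BDI submitted early?**
   - The BDI is done only in clinic. There is no delay, but this needs an exception that section 5.3.1 does not contain.
   - The BDI is reviewed on completion wherever it is done. There is no delay, but the coordinator must learn of the submission, and no means is described.
   - A BDI done early is reviewed at the visit. There is a delay of unknown length. The wording does not favour this reading, but it does not exclude it.

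8. **Do other procedures cover the interval?** Not clearly. Adverse events are assessed at the 6- and 12-month visits (section 6.1). Immediate alerts concern serious events that are study-related or result in death (section 6.2). The route to the site study doctor in section 10.2 appears under reactions to genetic results and depends on the participant's distress becoming known.

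**The case against.** The strongest reply is that the specific provision governs the general one. Section 6.1 is the only procedure written for the BDI, and it puts the instrument at the visit with immediate review. Section 5.3.1 is a general sentence about surveys. Read that way, the sections fit together, and delay arises only if staff disregard the word calling for immediate review. Coordinators also have REDCap access and give participants directions for using the system, so a remote submission is visible to the role that must act on it.

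Much of this stands. It rules out calling the sections a flat contradiction. A reader might infer that the protocol directs an early answer to be left unread, or that only an untimed central review would ever see it. The documents support neither inference: two natural readings of section 6.1 avoid delay, and coordinators can open the data themselves.

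What does not stand is that nothing remains to be fixed. The permission in section 5.3.1 is explicit and without exception, and access to a database does not tell anyone that a new answer has arrived.

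It is also fair to say that absence from the supplied text is not absence from the plan. Appendix O and the site protocol were not supplied and could state how the BDI is presented and handled. The wording of the suicidality item is not in the supplied copy of section 6.1 either; nothing is inferred from that gap.

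**Conclusion.** The inconsistency is real but modest. Section 5.3.1 permits the 6-month BDI to be completed before the visit, section 6.1 ties its administration and suicidality review to the visit, and the supplied text describes nothing that prompts a coordinator to read an early submission. A delayed review is therefore possible, if staff treat the review as a visit task.

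The size cannot be given. The documents do not say how many participants complete surveys early, how often ideation is reported, or how long before the visit a survey may be submitted. A reader might take everyone still enrolled at 6 months as the number affected. That would count only those to whom the option is open and would say nothing about who is at risk.

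The conclusion assumes that Appendix O and the site protocol do not already settle the matter. It is a minor safety clarification, with medium confidence because those documents were not available.

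**What to change.** - **Section 5.3.1, 6-month visit:** add a sentence excepting the BDI from the before-visit option, so that it is completed in clinic at the 6-month visit. The other surveys can keep the option.
- **Section 6.1:** add a sentence stating that the coordinator reviews the completed BDI before the participant leaves the clinic.

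This changes a stated rule for one instrument and leaves endpoints, sample size and analysis alone. The cost is two sentences and a few extra minutes of clinic time at one visit.

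If the sponsor prefers to keep remote completion, the alternative is a REDCap alert to the coordinator on the suicidality item with same-day review. That costs more, because the alert must be set up and a coordinator must be available to act the same day. If Appendix O or the site protocol already contains such a rule, a cross-reference in both sections is enough.
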